2.8.4 Other safety data

2.8.4.1 ECG and cardiac imaging data

Data handling

In case the study requires ECG replicates at any assessment, the average of the ECG parameters at that assessment should be used in the analyses.

Data analysis

12-lead ECGs including PR, QRS, QT, QTcF, and HR intervals will be obtained for each patient during the study. ECG data will be read and interpreted locally.

The number and percentage of patients with notable ECG values will be presented by cohort.

- QT, QTcF, or QTcB
 - New value of > 450 and ≤ 480 ms
 - New value of > 480 and ≤ 500 ms
 - New value of > 500 ms
 - Increase from Baseline of > 30 ms to ≤ 60 ms
 - Increase from Baseline of > 60 ms
- HR
 - Increase from baseline $> 25\%$ and to a value > 100 bpm
 - Decrease from baseline $> 25\%$ and to a value < 50 bpm
- PR
 - Increase from baseline $> 25\%$ and to a value > 200 ms
 - New value of > 200 ms
- QRS
 - Increase from baseline $> 25\%$ and to a value > 120 ms
 - New values of QRS > 120 ms

Categorical Analysis of QT/QTc interval data based on the number of patients meeting or exceeding predefined limits in terms of absolute QT/QTc intervals or changes from baseline will be presented. In addition, a listing of these patients will be produced by cohort.

A listing of all ECG assessments will be produced by cohort and notable values will be flagged. In the listing, the assessments collected during the post-treatment period will be flagged.

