- Section 7.1.2.2: Revised to remove capture of prescreening patients in database
- Section 7.1.2.3: Revised demographics collected based on CRF availability
- Section 7.1.4: Revised tumor assessments to be collected every 12 weeks
- Section 7.1.7: Revised tumor assessments to be collected every 12 weeks and revised eCRF page
- Section 7.1.8: Paragraph was deleted since it was duplicated from section 7.2.1.2
- Section 7.1.10: Revised eCRF page
- Section 7.2.1.1: Removed whole body scan and revised tumor assessments to be collected every 12 weeks
- Table 7-2: Removed whole body scan and revised tumor assessments to be collected every 12 weeks
- Section 7.2.2.5: Added RBG testing
- Table 7-4: Removed fasting criteria for partial chemistry labs
- Section 7.2.2.5.3: Added random glucose testing
- Section 7.2.3.1.3: Revised to add information regarding optional testing
- Table 7-5: Deleted ECG at every 3 cycles
- Section 10: Clarified primary and final analyses
- Section 10.4: Revised to include cohort C patient population
- Section 10.4.2: Revised to include cohort C patient population
- Table 10-1: Revised confidence intervals
- Section 10.5: Revised secondary objectives confidence intervals
- Section 10.5.1.6: Added overall survival
- Section 10.7: Revised to include additional interim analysis
- Section 10.8: Revised confidence intervals and updated sample size
- Table 10-2: Updated Operating Characteristics
- Section 11.3: Revised fetotoxic potential
- Section 13: Added reference for SOLAR-1

IRBs/IECs

A copy of this amended protocol will be sent to the Institutional Review Board (IRBs)/Independent Ethics Committee (IECs) and Health Authorities.

The changes described in this amended protocol require IRB/IEC approval prior to implementation.

The changes herein affect the Informed Consent. Sites are required to update and submit for approval a revised Informed Consent that takes into account the changes described in this protocol amendment.

Amendment 2 (02-May-2018)

Amendment rationale

The first study patient was screened on 14-Aug-2017 and as of 02-May-2018, 30 patients have been enrolled in the study CBYL719X2402.

The current amendment is intended to clarify the use of goserelin or leuprolide (LHRH agonists) as study treatment for pre-menopausal women (as applicable) and men (cohort B).

Changes to the protocol

- Updated glossary of terms due to EEA General Data Protection Regulation (GDPR)

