1.2.4.3 Clinical pharmacokinetics

The pharmacokinetics of alpelisib has been studied in healthy volunteers and adult patients with solid tumors. Steady-state alpelisib maximum plasma concentration (Cmax) and AUC increased proportionally over the dose range of 30 mg to 450 mg (0.1 to 1.5 times the approved recommended dosage) under fed conditions. The mean accumulation of alpelisib is 1.3 to 1.5 fold and steady-state plasma concentrations are reached within 3 days following daily dosage. In adult subjects who received alpelisib 300 mg once daily in the SOLAR-1 trial, mean steady-state alpelisib [coefficient of variation (CV%)] Cmax was 2480 (23%) ng/mL and AUC0-24hr was 33224 (21%) ng*h/mL based on a population PK approach. The median time to reach peak plasma concentration (Tmax) ranged between 2.0 to 4.0 hours. The half-life of alpelisib is predicted to be 8 to 9 hours. The mean (%CV) clearance of alpelisib is predicted to be 9.2 L/hr (21%) under fed conditions.

A high-fat high-calorie meal (985 calories with 58.1 g of fat) increased alpelisib AUC by 73% and Cmax by 84%, and a low-fat low-calorie meal (334 calories with 8.7 g of fat) increased alpelisib AUC by 77% and Cmax by 145% following a single dose of alpelisib. No clinically significant differences in alpelisib AUC were observed between low-fat low-calorie and high-fat high-calorie meals. Alpelisib can be co-administered with acid reducing agents, as long as it is taken after food, since food exhibited a more pronounced effect on the solubility of alpelisib than the effect of gastric pH.

Alpelisib is primarily metabolized by chemical and enzymatic hydrolysis to form its metabolite BZG791 and to a lesser extent by CYP3A4 in vitro. Following a single oral dose of 400 mg radiolabeled alpelisib under fasted condition, 81% of the administered dose was recovered in feces (36% unchanged, 32% BZG791) and 14% (2% unchanged, 7.1% BZG791) in urine. CYP3A4-mediated metabolites (12%) and glucuronides amounted to approximately 15% of the dose. Excretion of unchanged alpelisib occurs primarily via hepatobiliary export and/or intestinal secretion of alpelisib. As alpelisib is a substrate of BCRP, its elimination may be affected when co-administered with BCRP inhibitors.

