2.6.3 Risk management strategies

The risk to subjects in this trial will be minimized by compliance with the eligibility criteria and study procedures, close clinical monitoring, recommendations for concomitant medications, guidance for prohibited medications and dose adjustments or interruptions or discontinuations as outlined in Section 6.3. There may be unforeseen risks with alpelisib in combination with fulvestrant or letrozole.

Patients in this study will be carefully monitored for key toxicities that have been observed with alpelisib (see Section 1.2.4) with combination of fulvestrant or letrozole (see Section 1.2.1) with the following assessments (see Section 7): periodic laboratory, renal and liver function, urinallysis and ECG.

Risk will be further minimized by adherence to inclusion/exclusion selection criteria (see Section 5), avoidance of prohibited medication (see Section 6.4.4), close safety monitoring (see Section 8.1) and dose adjustment guidelines (see Section 6.3) for alpelisib and fulvestrant [Faslodex® prescribing information], letrozole prescribing information [Femara® Prescribing Information, Novartis] goserelin and leuprolide [Zoladex® prescribing information] and [Lupron® prescribing information].

A Steering Committee (SC) (see Section 8.7) will be established comprising investigators and Novartis personnel participating in the trial to ensure transparent management of the trial according to the protocol. A Novartis Safety Management Team (SMT) periodically reviews and evaluates all emerging safety data across the alpelisib program for early detection of potential safety signal assessment in a timely manner.

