7.2.2.7 Cardiac assessments

7.2.2.7.1 Electrocardiogram (ECG)

A standard 12 lead ECG will be performed after the patient has been resting for 5-10 min prior to each time point during the Core Phase indicated in Table 7-6.

Table 7-6 Local ECG collection plan

Cycle	Patients	Day	Time	ECG Type
Screening	All	Day -21 to -1	Anytime	12 Lead
Cycle 1	All	Day 1	Pre-dose	12 Lead
EOT (Core Phase)	All	N/A	Anytime	12 Lead
Unscheduled san	nple as clinical	ly indicated	Anytime	12 Lead

[figure not shown]
Interpretation of the tracing must be made by a qualified physician and documented on the ECG eCRF page. Each ECG tracing should be labeled with the study number, patient initials (where regulations permit), patient number, date, and kept in the source documents at the study site. Clinically significant abnormalities present at screening should be reported on the Medical History eCRF page. Clinically significant findings must be discussed with Novartis prior to enrolling the patient in the study. New or worsened clinically significant findings occurring after informed consent must be recorded on the Adverse Events eCRF page.

Additional, unscheduled, safety ECGs may be repeated at the discretion of the investigator at any time during the study as clinically indicated. Unscheduled ECGs with clinically significant findings should be collected. Local cardiologist ECG assessment may also be performed at any time during the study at the discretion of the investigator.

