10.5.2.4 Other safety data

Summary statistics for data from other tests will be provided, notable values will be flagged, and any other information collected will be listed as appropriate.

- ECGs: 12-lead ECGs including PR, QRS, QT, QTcF, and HR intervals will be obtained for each subject during the study. ECG data will be read and interpreted locally.
- Categorical Analysis of QT/QTc interval data based on the number of subjects meeting or exceeding predefined limits in terms of absolute QT/QTc intervals or changes from baseline will be presented. In addition, a listing of these subjects will be produced by cohort.
- ECOG: Shift tables to compare baseline to the worst on-treatment value.

- Cardiac imaging: change from baseline to worst post-baseline in LVEF values.
- Vital signs: Data on vital signs will be tabulated and listed, notable values will be flagged.

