- 3. If the patient discontinues fulvestrant on or after Cycle 2 Day 1, then:
 - the last date of exposure to fulvestrant is calculated as (last date of administration of fulvestrant) + (length of time interval - 1) i.e. [last date of fulvestrant administration+ (28-1)].
 - If the patient died or was lost to follow-up within last date of administration of fulvestrant + 27 days, the last date of exposure to fulvestrant is the date of death or the date of last contact, respectively.

Goserelin and Leuprolide

Goserelin and leuprolide were administered (for pre menopausal women and men (cohort B)) on the first day of every cycle (e.g. Cycle 1 Day 1, Cycle 2 Day 1 etc.)

The *last date of exposure to* Goserelina or leuprolide is calculated as follows:

- (last date of administration of Goserelina or leuprolide) + (length of time interval - 1) i.e. [last date of Goserelina or leuprolide administration+ (28-1)].
- If the patient died or was lost to follow-up within last date of administration of Goserelina or leuprolide + 27 days, the last date of exposure to Goserelina or leuprolide is the date of death or the date of last contact, respectively.

Study day

The study day, describes the day of the event or assessment date, relative to the reference start date.

The study day is defined as:

- The date of the event (visit date, onset date of an event, assessment date etc.) – reference start date + 1 if event is on or after the reference start date;
- The date of the event (visit date, onset date of an event, assessment date etc.) – reference start date if event precedes the reference start date.

The reference date for all assessments (safety, efficacy, etc) is the start of any component of the study treatment.

Time unit

A year length is defined as 365.25 days. A month length is 30.4375 days (365.25/12). If duration is reported in months, duration in days will be divided by 30.4375. If duration is reported in years, duration in days will be divided by 365.25.

Baseline

For safety and efficacy evaluations, the last available assessment on or before the date of start of study treatment is defined as “baseline” assessment.

If patients have no value as defined above, the baseline result will be missing.

On-treatment assessment/event and observation periods

For adverse event reporting the overall observation period will be divided into three mutually exclusive segments:

- ***pre-treatment period:***

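### The QT/QTc outlier tables are insensitive to an alpelisib effect: no ECG is scheduled during dosing after the pre-dose baseline, and late end-of-treatment ECGs count as on-treatment

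*SAP*

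**What the plan says.** Protocol 10.5.2.4 and SAP Amendment 4, Section 2.8.4.1, plan the same analysis. The SAP words it as a "Categorical Analysis of QT/QTc interval data based on the number of patients meeting or exceeding predefined limits", and the protocol as a "Categorical Analysis of QT/QTc interval data based on the number of subjects meeting or exceeding predefined limits". The SAP adds the categories: new QT/QTc values above 450, 480 and 500 ms, and increases from baseline above 30 and 60 ms. Results are presented by cohort.

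Protocol 7.2.2.7.1 has ECGs done "prior to each time point during the Core Phase indicated in Table 7-6". That table lists screening, Cycle 1 Day 1 pre-dose, Core Phase EOT at any time of day, and unscheduled ECGs when clinically indicated. The ECG row of Table 7-1 agrees.

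Three SAP rules decide what enters the tables:

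- Baseline is "the last available assessment on or before the date of start of study treatment" (SAP 2.1.1). Where the Cycle 1 Day 1 pre-dose ECG exists, it is the baseline.
- The on-treatment period ends 30 days after the last administration of any study treatment component (SAP 2.1.1).
- Percentages use the number of patients in the relevant population (SAP 2.1), which for safety is the Safety Set (SAP 2.8). Section 2.8.4.1 does not require a post-baseline ECG.

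On exposure, protocol 1.2.4.3 states: "The half-life of alpelisib is predicted to be 8 to 9 hours".

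**The concern.** A table of QT/QTc outliers is normally read as describing patients on drug. Here EOT is the only scheduled post-baseline ECG, and much of the time allowed for it is free of alpelisib. The 30-day rule still places those ECGs in the on-treatment summary, where they pull the outlier rate down. Patients with no post-baseline ECG can lower it further, because they may stay in the denominator.

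The remaining on-drug ECGs come from two uneven sources. Unscheduled ECGs are taken on clinical indication, and protocol 7.2.2.7.1 asks for collection of those with clinically significant findings. Patients treated before Amendment 3 may also have ECGs from a schedule that the amendment then changed ("Table 7-5: Deleted ECG at every 3 cycles"). That log entry is not a conflict with the current text; it only shows how the data accrued.

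The stake is interpretation. A low outlier rate could be presented as on-treatment safety evidence when it largely describes ECGs without alpelisib exposure.

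**Working it through.** The documents state no figure for the ECG analysis, so there is none to reproduce. The check reads the schedule against the SAP definitions and then computes washout.

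**Inputs**

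- Alpelisib half-life 8 to 9 h; median time to peak 2 to 4 h (protocol 1.2.4.3).
- EOT at most 21 days after last dose (Table 7-1), or 7 days (Appendix 5, Section 4.2). Protocol 7.1 asks patients who stop treatment to return promptly for EOT.
- Fulvestrant half-life 40 to 50 days (1.2.2.1); letrozole 2 days (1.2.1.1).
- The partner drug may continue after alpelisib stops (6.1.4).
- 127 patients enrolled by 22-Jan-2019, just before Amendment 3; 380 in total.

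**Step 1. Alpelisib remaining.** Fraction of peak = 2^(-t / half-life).

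| Time since peak | 8 h half-life | 9 h half-life |
|---|---|---|
| 12 h | 35.4% | 39.7% |
| 24 h | 12.5% | 15.7% |
| 48 h | 1.6% | 2.5% |
| 7 days | under 0.001% | under 0.001% |
| 21 days | 63 half-lives | 56 half-lives |

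**Step 2. Time with at least 10% of peak.** t = half-life × log2(10) = half-life × 3.32, giving 26.6 h (8 h) and 29.9 h (9 h).

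**Step 3. Share of the EOT window**, if visits are evenly spread (assumption):

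- 21 days = 504 h: 26.6/504 = 5.3%; 29.9/504 = 5.9%.
- 7 days = 168 h: 26.6/168 = 15.8%; 29.9/168 = 17.8%.

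Counting from the dose instead of the peak adds 2 to 4 h. The interval becomes 28.6 to 33.9 h, and the shares become 5.7-6.7% and 17.0-20.2%. Prompt EOT visits would raise all of these. Continuing the partner drug alone would lower them, because time off alpelisib could then exceed 21 days.

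**Step 4. Partner drugs at 21 days.** Fulvestrant: 2^(-21/40) = 69.5% to 2^(-21/50) = 74.7% remaining. Letrozole: 2^(-21/2) = 0.07%. The point is therefore about alpelisib; a late EOT ECG in Cohorts A and C is still taken with fulvestrant present.

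**Step 5. ECGs under the earlier schedule.** 127/380 = 33.4% were enrolled just before Amendment 3. This is not a count of patients with on-drug ECGs. Some of the 127 may have stopped before reaching one, and some enrolled later may have started before their site implemented the amendment. Cohort C was added by the same amendment, so it has no scheduled ECG during dosing after the first dose.

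**The case against.** The strongest objection is that the tables can still show a QT effect. The EOT limit is an upper bound, and an ECG on the day of the last dose or the day after still carries exposure. Unscheduled on-drug ECGs enter the tables, as do ECGs from the earlier schedule, because the SAP uses all data in the database. This stands. A reader might infer that the tables cannot detect a drug effect on QT, and the documents do not support that. They support low sensitivity and uneven ascertainment. Marked prolongations can appear, but the rate is hard to interpret.

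Second, even spacing of EOT visits is not something the documents state. This also stands, and it is why both windows are shown. The shares illustrate the problem and do not estimate the actual visit pattern.

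Third, the study is non-comparative and results are shown by cohort, so uneven ascertainment biases no planned comparison. That is correct. The mixing within Cohorts A and B and the gap in Cohort C remain. A reader might also infer that the other 67% of patients have no scheduled on-drug ECG; the enrolment count does not establish that.

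Fourth, protocol 2.6.3 lists "periodic laboratory, renal and liver function, urinallysis and ECG" among the monitoring assessments, and one might read this as a promise of periodic ECGs. The first word need not govern the last item, and the sentence refers to Section 7 for the schedule. No broken commitment is shown.

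Finally, QT is not an endpoint in Table 3-1, safety rests mainly on adverse events and laboratory values, nonclinical cardiac studies showed no electrophysiological risk, and neither document plans a negative QT conclusion. This limits the importance of the point but does not make the table informative as specified.

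**Conclusion.** The concern holds in a limited form. The current protocol schedules no ECG during dosing after the pre-dose baseline. The SAP's 30-day on-treatment rule and the lack of an evaluable denominator let alpelisib-free EOT ECGs, and patients without a post-baseline ECG, dilute the QT/QTc outlier rates.

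On the 10%-of-peak criterion, exposure covers about 5-6% of a 21-day EOT window or 16-18% of a 7-day window. These figures assume first-order elimination at the stated half-life and evenly spread visits. Insensitivity over most of the allowed time does not depend on which window applies, although many EOT visits close to the last dose would ease it.

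The conclusion concerns alpelisib. Calling the EOT ECGs drug-free would be wrong for the fulvestrant cohorts. It is a reporting weakness in a supporting safety table and does not affect the efficacy conclusions.

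**What to change.** In SAP 2.8.4.1:

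- Present the notable-ECG and categorical QT tables by time since last alpelisib dose (while dosing or shortly after, versus later), with the boundary fixed in advance. The washout figures point to one to two days.
- Within each category, separate scheduled from unscheduled ECGs.
- Use as denominator the patients with a baseline and at least one post-baseline ECG in that category, and show that n by cohort.
- Keep the all-data table as supportive.

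State in the CSR that the current protocol schedules no ECG during dosing after the first dose, so a low outlier rate is not evidence of no alpelisib effect. The 21-day EOT limit in Table 7-1 and the 7-day limit in Appendix 5 must be reconciled.

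Splitting is safer than restricting to one table of ECGs near dosing. Such a table would be enriched for clinically indicated ECGs and could overstate the rate.

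The cost is SAP wording and reprogrammed tables from data already collected, with no new visits. The evaluable numbers will be small, and the on-dosing rates may be biased upward by clinically indicated ECGs, so both should be stated beside the table.

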2.8.4.2 Vital signs

Vital sign assessments are performed in order to characterize basic body function. The following parameters were collected: height (cm), weight (kg), body temperature ($^{\circ}\text{C}$), heart rate (beats per minute), systolic and diastolic blood pressure (mmHg).

Data handling

Vital signs collected on treatment will be summarized. Values measured outside of on treatment period will be flagged in the listings.

Data analysis

For analysis of vital signs the clinically notable vital sign criteria are provided in [Table 2-7](#) below.

Table 2-7 Clinically notable changes in vital signs

Vital sign (unit)	Clinically notable criteria	
	above normal value	below normal value
Weight (kg)	increase $\geq 10\%$ from Baseline	decrease $\geq 10\%$ from Baseline
Systolic blood pressure (mmHg)	≥ 180 with increase from baseline of ≥ 20	≤ 90 with decrease from baseline of ≥ 20

Vital sign (unit)	Clinically notable criteria	
	above normal value	below normal value
Diastolic blood pressure (mmHg)	>=105 with increase from baseline of >=15	<=50 with decrease from baseline of >=15
Pulse rate (bpm)	>=100 with increase from baseline of >25%	<=50 with decrease from baseline of > 25%
Body temperature	>= 39.1	-

The number and percentage of patients with notable vital sign values (high/low) will be presented by cohort.

A listing of all vital sign assessments will be produced by cohort and notable values will be flagged. In the listing, the assessments collected outside of on-treatment period will be flagged.

2.8.4.3 Cardiac imaging (MUGA / ECHO)

For left ventricular ejection fraction (LVEF) a shift table using CTC grades for 'Ejection fraction - decrease' as defined per CTCAE version v4.03 to compare baseline to the worst on-treatment value will be provided.

A listing of patients with newly occurring clinically significant abnormality will be produced by cohort.

Note: If there is any change in the methodology used throughout the study compared to baseline, the post-baseline values for which the methodology differs from baseline will be discarded in the tables presenting comparisons to baseline.

2.8.4.4 ECOG performance status

ECOG Performance status (PS) is assessed to attempt to quantify the impact of disease on daily life activities of patients.

ECOG PS scale is used to assess physical health of patients, ranging from 0 (most active) to 5 (least active) (see Table 7-4 of the study protocol for details).

Shift tables will be produced to compare baseline to the worst on-treatment value.

